^l Viral loads of BKV, AdV, CMV, JCV, and HHV-6 in plasma and of EBV in PCMBs will be measured weekly for adult patients and pediatric patients ≥ 12 years old after allogenic HCT conditioning during pre-screening period and screening period until treatment assignment, if possible. Pediatric patients < 12 years old will have only one blood draw during the Screening visit and will not have weekly blood draws during the screening period. Viral load testing should NOT be done on day of HCT during pre-screening. The results of the repeat analyses from the screening period must be available at the time of treatment assignment, unless the timing of the Screening Visit is 1 week or less before treatment administration. Results of central laboratory testing for viral load will be used for the purpose of determining eligibility/inclusion.

^m Adult patients and pediatric patients ≥ 12 years old only

Table 2: Schedule of Activities – Treatment -- Period 1 for Patients ≥12 Years of Age (Week 1 to 14, All Cohorts)

Time Period	Treatment Assignment	Study Drug Administration Day	Treatment Period													
			Wk 1	Wk 2	Wk 3	Wk 4	Wk 5	Wk 6	Wk 7	Wk 8	Wk 9	Wk 10	Wk 11	Wk 12	Wk 13	Wk 14
Study Day		1 ^a	8	14	21	28	35	42	49	56	63	70	77	84	91	98
Visit Window (Days)		NA ^b	±3	±5	±3	±5	±3	±5	±3	±5	±3	±5	±3	±5	±3	±3
Study Procedures																
Review of I/E criteria		X														
Prior & concomitant medications as well as conditioning regimen for HCT		X		X		X		X		X		X		X		X
Adverse events ^c		X		X		X		X		X		X		X		X
Physical examination ^d		X		X		X		X		X		X		X		X
Weight		X			X			X			X			X		X
Vital signs ^e		X		X		X		X		X		X		X		X
12-lead ECG ^f		X		X		X		X		X		X		X		X
Clinical labs ^g		X		X		X		X		X		X		X		X
Pregnancy test ^h		X		X		X		X		X		X		X		

Time Period	Treatment Assignment	Study Drug Administration Day	Treatment Period													
			Wk 1	Wk 2	Wk 3	Wk 4	Wk 5	Wk 6	Wk 7	Wk 8	Wk 9	Wk 10	Wk 11	Wk 12	Wk 13	Wk 14
Study Day		1 ^a	8	14	21	28	35	42	49	56	63	70	77	84	91	98
Visit Window (Days)		NA	±3	±5	±3	±5	±3	±5	±3	±5	±3	±5	±3	±5	±3	±3
Study Procedures																
BKV, AdV, CMV, JCV, and HHV-6 viral load ⁱ			X	X	X	X	X	X	X	X	X	X	X	X	X	X
EBV PCMBs ⁱ		X	X	X	X	X	X	X	X	X	X	X	X	X	X	X
Treatment Assignment ^j	X															
Virus-Specific T Cell Assessment ^k		X				X		X			X			X		X
Study treatment administration ^l		X		X		X		X		X		X		X		
Post infusion monitoring ^m		X		X		X		X		X		X		X		
Infection assessment ⁿ		X	X	X	X	X	X	X	X	X	X	X	X	X	X	X

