2.2.2. Overview of Clinical Studies with Virus-Specific T Cells

2.2.2.1. Results of the CHARMS Study with Third Party-Derived Multivirus-Specific T Cells, ALVR105

To investigate the safety and clinical efficacy of ALVR105, a multivirus-specific T cell product reactive for BKV, AdV, HHV-6, EBV, and CMV generated from third-party, healthy, eligible donors, a Phase 1/2a clinical study was conducted in recipients of allogeneic HCT with drug-refractory infections with ≥ 1 of the 5 viruses targeted by ALVR105 (Tzannou, 2017). In this study, patients received a single IV infusion of 2×10^7 partially HLA-matched ALVR105 cells/m², with the option to receive a second infusion after 4 weeks (actual range 14 days to >6 weeks) and additional infusions at biweekly intervals thereafter. Therapy with standard antiviral medications could be continued at the discretion of the treating physician (Tzannou, 2017).

A total of 58 patients with drug-refractory infections following allogeneic HCT were infused with ALVR105 cell lines matched at 1 to 6 HLA antigens; 54 of these patients completed study treatment and the initial 28-day safety follow-up (the first 38 patients to complete the study are reported in Tzannou et al, 2017. Of the 71 total infections treated, 25 (35.2%) infections were BKV and 24 (33.8%) infections were CMV. Of the 58 patients who were treated (one of whom had 2 courses of treatment), 48 patients were treated for a single virus, 10 patients were treated for 2 viral infections, and 1 patient was treated for infections by 3 different viruses.

All infusions were well tolerated. None of the patients developed cytokine release syndrome (CRS). In the weeks after infusion, 1 patient developed recurrent Grade 3 gastrointestinal (GI) GVHD following rapid systemic corticosteroid taper, and 8 patients developed recurrent ($n = 4$) or de novo ($n = 4$) Grade 1 to 2 skin GVHD, which resolved with the administration of topical treatments ($n = 7$) and reinitiation of systemic corticosteroids after taper ($n = 1$). Between 3 and 6 months after infusion, 2 patients experienced a flare of upper GI GVHD, which resolved after a brief systemic corticosteroid course.

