8.1.3. Treatment period

The treatment period is 14 weeks. Study therapy (with ALVR105 or placebo) will begin between 15 and 42 (+7) days (inclusive) post-HCT. Study therapy will be given at 2-week intervals through Week 14, and the study evaluation will continue through Week 26 (~6 months). The first 25 to 35 patients (Cohort OL) will be assigned to ALVR105 for 30 days of open-label dosing [REDACTED].

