8.1.4. Follow-up period

The follow-up period is for 12 weeks with monthly visits. A telephone follow-up call will occur approximately 12 months (~52 weeks) after Week 26.

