8.5.1. Time Period and Frequency for Collecting AE and SAE Information

- All AEs and SAEs will be collected at the time points specified in the SoA ([Section 1.3](#)) from signing of informed consent until study participation is complete.
- Medical occurrences that begin before treatment assignment but after obtaining informed consent/assent will be recorded as Medical History/Current Medical Conditions, not as AEs.
- All SAEs will be recorded and reported to the Sponsor or designee immediately and under no circumstance should this exceed 24 hours, as indicated in Appendix 3 ([Section 10.3](#)). The Investigator will submit any updated SAE data to the Sponsor within 24 hours of it being available.
- Investigators are not obligated to actively seek information on AEs or SAEs after conclusion of the study participation. However, if the Investigator learns of any SAE,

including a death, at any time after a participant has been discharged from the study, and he/she considers the event to be reasonably related to the study intervention or study participation, the Investigator must promptly notify the Sponsor.

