9.5.1. Stopping Criteria

9.5.1.1. Stopping Criteria for Individual Patients

As GVHD and CRS are theoretical safety concerns associated with administration of third-party allogeneic T cells, the incidence and severity of GVHD and CRS will be monitored during the study.

No patients will be permitted to receive subsequent infusions of ALVR105 or placebo if:

1. They develop irreversible, life-threatening, Grade 3 to 4 acute GVHD within 6 weeks, or a Grade 3 to 4 non-hematologic AE within 4 weeks from last ALVR105 dose that is considered related to study treatment administration. If this occurs, the patient's toxicities will be followed until resolution or until the patient's participation in the study ends,
2. Receive any other hematopoietic stem cell product,
3. Receive therapy for relapse of the patient's primary malignancy,
4. Develop Grade 3 or 4 CRS that persists beyond 72 hours.

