9.5.1.2. Stopping Criteria for the Study

Treatment assignment will be halted if 3 patients experience SAEs that meet the following criteria:

- CTCAE Grade 3
- Considered related by the Investigator
- Occur during the Treatment Period following the initial dose
- Cannot be reasonably attributed to the patient's underlying disease, other medical condition, or concomitant medications

If this occurs, treatment assignment will not resume until there has been a thorough review of all safety data to date and concluded that it is safe for the study to continue.

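### The study-level halting rule stops counting related SAEs at Day 98, only about 14 days after the last scheduled infusion on Day 84

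*Protocol*

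**What the plan says.** **Study-level rule.** Protocol 9.5.1.2: "Treatment assignment will be halted if 3 patients experience SAEs that meet the following criteria". The criteria are CTCAE Grade 3, relatedness in the investigator's view, no reasonable alternative attribution, and a time limit: "Occur during the Treatment Period following the initial dose". Assignment resumes only after a review of all safety data.

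**Length of the period.** Section 8.1.3: "The treatment period is 14 weeks". The schedules put Week 14 at Day 98. What comes next is a separate period (8.1.4): "The follow-up period is for 12 weeks with monthly visits".

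**Last infusion.** In the treatment-period schedules (section 1.3, Tables 2 and 3) the row "Study treatment administration" is marked at Day 1 and Weeks 2, 4, 6, 8, 10 and 12, and is blank at Week 14. Sections 4.1 and 8.1.3 describe two-weekly dosing through Week 14, and 6.5.1 refers to a last dose after Week 14.

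**Patient-level rule.** Sections 7.1 and 9.5.1.1 bar further infusions in several situations, including: "They develop irreversible, life-threatening, Grade 3 to 4 acute GVHD within 6 weeks, or a Grade 3 to 4 non-hematologic AE within 4 weeks" of the last ALVR105 dose, where considered related to study treatment.

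**Collection.** Under 8.5.1, AEs and SAEs are collected "from signing of informed consent until study participation is complete". Even for patients who have discontinued, the schedule footnotes keep drug-related and fatal SAEs under collection to Week 26.

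**The concern.** The counting period ends on a visit-schedule boundary, not at a set time after the last exposure. A patient who completes the course has had every planned infusion by Day 84, yet a related SAE on, say, Day 105 cannot contribute to the trigger. By then the patient-level rule has no infusion left to withhold, so among the rules written into the protocol only the study-level one could use the event to protect others. It could matter: section 4.1 expects enrollment to last about 12 months, so assignment may still be open when early patients pass Day 98. With a threshold of 3 patients, one uncounted event can decide whether the pause happens.

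**Working it through.** The documents give no operating characteristics for the halting rule, so there is no stated figure to reproduce. The check is calendar arithmetic followed by a labelled illustration.

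**Inputs**
- Infusions on Days 1, 14, 28, 42, 56, 70 and 84; Week 14 = Day 98 (schedules, section 1.3).
- Benchmark post-dose periods of 28 days (related non-hematologic AE) and 42 days (severe acute GVHD), from 7.1 and 9.5.1.1.
- Threshold of 3 patients (9.5.1.2); Cohort OL of 25 to 35 patients (4.1).

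**Step 1: time covered after the last infusion.** 98 − 84 = 14 days. The SAP's analysis windows number these visits Day 85 and Day 99; the difference is the same.

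**Step 2: time not covered.** Days outside = (infusion day + window length) − 98, if positive.

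| Infusion | 4-week window ends | Days outside | 6-week window ends | Days outside |
|---|---|---|---|---|
| Day 56 | 84 | 0 | 98 | 0 |
| Day 70 | 98 | 0 | 112 | 14 of 42 |
| Day 84 | 112 | 14 of 28 | 126 | 28 of 42 |

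Windows after earlier infusions lie wholly inside. A patient who stops dosing early is therefore little affected: an SAE still counts if it occurs by Day 98.

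**Step 3: sensitivity to visit windows.** The tables allow ±5 days at Week 12 and ±3 days at Week 14. If the period is taken to end at the Week 14 visit, the part of the 4-week window left outside runs from 79 + 28 − 101 = 6 days to 89 + 28 − 95 = 22 days.

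**Step 4: if the last infusion is at Week 14.** 98 + 28 = 126, so all 28 days fall outside.

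**Step 5: illustration of the effect on the trigger.** Let p be the chance that a patient has a qualifying SAE by Day 112. Assume a constant hazard from first dose to Day 112; then 14/112 = 12.5% of events fall after Day 98, and the countable rate is 0.875p. The chance of reaching the threshold is P(X ≥ 3) = 1 − Σ(k = 0 to 2) C(n,k) q^k (1 − q)^(n−k), with q = p or q = 0.875p.

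| n | Assumed p | All events count | Count stops at Day 98 |
|---|---|---|---|
| 25 | 10% | 0.463 | 0.376 |
| 30 | 5% | 0.188 | 0.142 |
| 30 | 10% | 0.589 | 0.495 |
| 30 | 20% | 0.956 | 0.916 |
| 35 | 10% | 0.694 | 0.601 |

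The values of p and the constant hazard are assumptions; the documents give neither. The n values span the stated size of Cohort OL and serve only as a scale, because the rule is not limited to that cohort.

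**The case against.** **The two rules serve different purposes.** The 4- and 6-week periods decide whether one patient may be dosed again, and the last dose there most naturally means the most recent one. A reader might infer that the protocol contradicts itself, or that these windows are its definition of dose-limiting toxicity. The documents support neither: they contain no such definition, and a redosing rule and an assignment pause need not share a time base. The windows are only a benchmark for how long after a dose the protocol regards toxicity as potentially dose-related. In that role they stand.

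**The GVHD comparison is not like for like.** The patient rule requires irreversible, life-threatening Grade 3 to 4 acute GVHD; 9.5.1.2 counts CTCAE Grade 3 SAEs, and section 10.3.3 places life-threatening events at CTCAE Grade 4. The time limit may not be what excludes such an event. The 28-of-42-day figure is thus correct arithmetic but does not carry the point.

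**Earlier clinical data do not show the gap matters.** The CHARMS summary (2.2.2.1) reports: "Between 3 and 6 months after infusion, 2 patients experienced a flare of upper GI GVHD". That is later than both windows, and the flares resolved after a brief steroid course. They are not stated to be related or Grade 3, and under Table 6 upper GI involvement alone does not exceed Grade II.

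**Late events are still overseen.** SAEs are reported within 24 hours (8.5.1), SUSARs are expedited (8.5.4.1), and the DSMB reviews safety throughout the study (10.1.5.2) and receives summaries of all SAEs (SAP 3.6). It would be wrong to infer that late SAEs go unseen. What remains is that no supplied text lets them count toward this trigger. The one DSMB review with a stated time (9.5) comes after 30 days of treatment, well before Day 84, and the charter was not available.

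**Cohort OL is past.** The SAP introduction says its patients were already enrolled, treated and followed, so a change can help only later assignment. This is correct and limits the reach of the point.

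**Conclusion.** The point holds as a gap in coverage, not as a contradiction. As written, the trigger covers about 14 days after the Day 84 infusion. Against the protocol's own 4-week benchmark, 14 of 28 days are left out: 6 to 22 days once visit windows are allowed for, and all 28 if dosing runs through Week 14.

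A reader might go further and say that half to two-thirds of late events are lost. That would apply only to events after the last infusion, only if they spread evenly over the 4- or 6-week window, and the upper figure rests on the unlike GVHD comparison. Over the whole course, a constant hazard to Day 112 puts 12.5% of events after Day 98. With an assumed 10% rate and 30 patients, the chance of reaching 3 falls from 0.589 to 0.495, a moderate loss that depends on those assumptions.

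The scope of the halt is a secondary wording matter. Section 9.5.1.2 pauses treatment assignment, yet its heading and closing sentence speak of the study. A reader might infer that patients already assigned are unprotected; sections 7.1, 8 and 9.5.1.1 cover them individually, so the documents do not support that. The text simply does not say whether their infusions fall within the halt.

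**What to change.** 1. Reconcile the counting period in 9.5.1.2 with the post-dose windows in 7.1 and 9.5.1.1 and with SAE collection to Week 26, so that related SAEs after the final infusion can count toward the trigger for cohorts still being assigned. The length of the period and its terms are for the sponsor and DSMB to set. If they prefer to leave later events to DSMB judgement, the protocol should say so and why.
2. Reconcile the schedules (last infusion Week 12) with sections 4.1, 6.5.1 and 8.1.3 (dosing through, or a last dose after, Week 14), because the uncovered time depends on it.
3. State whether the halt also covers infusions in patients already assigned.

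The cost is protocol wording, with the DSMB charter aligned if needed, and a slightly higher chance of a temporary pause. The SAEs concerned are already collected, so no new data are required.

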10. SUPPORTING DOCUMENTATION AND OPERATIONAL CONSIDERATIONS

10.1. Appendix 1: Regulatory, Ethical, and Study Oversight Considerations

10.1.1. Regulatory and Ethical Considerations

- This study will be conducted in accordance with the protocol and with the following:
 - Consensus ethical principles derived from international guidelines including the Declaration of Helsinki and Council for International Organizations of Medical Sciences (CIOMS) International Ethical Guidelines
 - Applicable International Council on Harmonisation (ICH) Good Clinical Practice (GCP) Guidelines
 - Applicable laws and regulations
- The protocol, protocol amendments, ICF, Investigator Brochure, and other relevant documents (eg, advertisements) must be submitted to an IRB/IEC by the Investigator and reviewed and approved by the IRB/IEC before the study is initiated.
- Any amendments to the protocol will require IRB/IEC approval before implementation of changes made to the study design, except for changes necessary to eliminate an immediate hazard to study participants.
- Protocols and any substantial amendments to the protocol will require health authority approval prior to initiation except for changes necessary to eliminate an immediate hazard to study participants.
- The Investigator will be responsible for the following:
 - Providing written summaries of the status of the study to the IRB/IEC annually or more frequently in accordance with the requirements, policies, and procedures established by the IRB/IEC
 - Notifying the IRB/IEC of SAEs or other significant safety findings as required by IRB/IEC procedures
 - Providing oversight of the conduct of the study at the site and adherence to requirements of 21 Code of Federal Regulations (CFR), ICH guidelines, the IRB/IEC, European regulation 536/2014 for clinical studies (if applicable), European Medical Device Regulation 2017/745 for clinical device research (if applicable), and all other applicable local regulations

10.1.2. Financial Disclosure

Investigators and sub-Investigators will provide the Sponsor with sufficient, accurate financial information as requested to allow the Sponsor to submit complete and accurate financial certification or disclosure statements to the appropriate regulatory authorities. Investigators are responsible for providing information on financial interests during the course of the study and for 1 year after completion of the study.

10.1.3. Informed Consent Process

- The Investigator or his/her representative will explain the nature of the study to the participant or their legally authorized representative and answer all questions regarding the study.
- Participants must be informed that their participation is voluntary. Participants or their legally authorized representative will be required to sign a statement of informed consent that meets the requirements of 21 CFR 50, local regulations, ICH guidelines, Health Insurance Portability and Accountability Act (HIPAA) requirements, where applicable, and the IRB/IEC or study center.
- The medical record must include a statement that written informed consent was obtained before the participant was enrolled in the study and the date the written consent was obtained. The authorized person obtaining the informed consent must also sign the ICF.
- Participants must be re-consented to the most current version of the ICF(s) during their participation in the study.
- A copy of the ICF(s) must be provided to the participant or their legally authorized representative.

10.1.4. Data Protection

- Participants will be assigned a unique identifier by the Sponsor. Any participant records or datasets that are transferred to the Sponsor will contain the identifier only; participant names or any information which would make the participant identifiable will not be transferred.
- The participant must be informed that his/her personal study-related data will be used by the Sponsor in accordance with local data protection law. The level of disclosure must also be explained to the participant who will be required to give consent for their data to be used as described in the informed consent
- The participant must be informed that his/her medical records may be examined by Clinical Quality Assurance auditors or other authorized personnel appointed by the Sponsor, by appropriate IRB/IEC members, and by inspectors from regulatory authorities.

10.1.5. Committee Structure

10.1.5.1. Clinical Adjudication Committee

The CAC will determine the definition of AdV, BKV, CMV, EBV, HHV-6, or JCV end organ disease (see CAC charter).

10.1.5.2. Data Safety Monitoring Board

A review by the DSMB will be done when approximately 30 patients have completed 30 days of treatment and throughout the study as indicated in the DSMB charter (see DSMB charter).

10.1.6. Dissemination of Clinical Study Data

Data generated by this study must be available for inspection by the FDA, the Sponsor or their designee, applicable foreign health authorities, and the IRB/IEC as appropriate. Patients or their legal representatives may request their medical information be given to their personal physician or other appropriate medical personnel responsible for their welfare.

Patient medical information obtained during the study is confidential and disclosure to third parties other than those noted above is prohibited.

10.1.7. Data Quality Assurance

- All participant data relating to the study will be recorded on printed or electronic CRF unless transmitted to the Sponsor or designee electronically (eg, laboratory data). The Investigator is responsible for verifying that data entries are accurate and correct by physically or electronically signing the CRF.
- Guidance on completion of CRFs will be provided in the Study Manual.
- The Investigator must permit study-related monitoring, audits, IRB/IEC review, and regulatory agency inspections and provide direct access to source data documents.
- Quality tolerance limits (QTLs) will be pre-defined to identify systematic issues that can impact participant safety and/or reliability of study results. These pre-defined parameters will be monitored during the study and important deviations from the QTLs and remedial actions taken will be summarized in the clinical study report.
- Monitoring details describing strategy (eg, risk-based initiatives in operations and quality such as Risk Management and Mitigation Strategies and Analytical Risk-Based Monitoring), methods, responsibilities and requirements, including handling of noncompliance issues and monitoring techniques (central, remote, or on-site monitoring) are provided in the Monitoring Plan.
- The Sponsor or designee is responsible for the data management of this study including quality checking of the data.
- The Sponsor assumes accountability for actions delegated to other individuals (eg, Contract Research Organizations).
- Records and documents, including signed ICFs, pertaining to the conduct of this study must be retained by the Investigator for 5 years after study completion unless local regulations or institutional policies require a longer retention period. No records may be destroyed during the retention period without the written approval of the Sponsor. No records may be transferred to another location or party without written notification to the Sponsor.

